Carnegie Mellon University

Study Protocol and Statistical Analysis Plan (SAP)

NCT04509024

Incidental Auditory Category Training for Language Learning

1R03HD099382-01

February 26, 2024

Carnegie Mellon University

Design Overview. We propose an 8-week training study among university students with no prior experience with Mandarin (or any tonal language). We will track learning through two modalities: explicit classroom instruction and web-based incidental training. Half of the participants will come

Table I	Incidental, Nonspeech (nonspeech)	Explicit, Speech (speech)	No Training (none)
Relevant Classroom, Mandarin L2 (+instruction)	+ instruction / nonspeech Preliminary Study 2	+ instruction / speech Preliminary Study 2	+ instruction / none
Irrelevant Classroom, French/Spanish L2 (-instruction)	- instruction / nonspeech Preliminary Study 1	- instruction / speech Prior literature	- instruction / none

from first-year Mandarin classes at Carnegie Mellon University (CMU). These students (+instruction, see **Table I**) will undergo traditional L2 learning through explicit instruction, as is the typical pedagogical approach of university classrooms. This approach emphasizes the four specific tonal contours and the lexical role of tone in Mandarin word recognition through explicit instruction. On average, these students will spend 200 minutes/week in classroom instruction, and an additional 300 minutes expected preparation outside of class. The other half of the participants will be recruited from the same university-student population, but will be engaged in non-Mandarin, non-tonal foreign language instruction for Spanish or French at an identical 200 minutes/week. In this manner, these participants (-instruction, **Table I**) will be similarly motivated to learn a foreign language, yet will have no tonal training: they will not be taught the four tone categories or the lexical role tone carries. In this way, the -instruction group models naïve participants typical of laboratory L2 training studies, with the added control of being an equally motivated cohort. Participants will undergo either supplementary incidental nonspeech training or supplementary explicit speech training. A third group will serve as a control and undergo no additional training.

Participants and Power. We will test 150 participants (N=25/condition). The sample size was selected so that multiple regression analyses with all predictors have high power ($1-\beta=0.8$, $p<0.05$, two-tailed) to detect even a small (Cohen's $f^2=0.08$) reliable deviation from 0 of a single linear regression coefficient (G*Power). This sample size is twice that of previous laboratory incidental L2 training studies (N=13, 80; N=10, 63), appreciating that we will need a somewhat larger sample to accommodate the potential for attrition across the retention interval. Even if we were to experience as much as 33% attrition, this sample size will assure a robust test (N=17; Cohen's $f^2=0.08$; power=.6) in line with prior research.

All participants will be native-English young adults (18-28 years) with normal hearing, no history of speech or language disorder, no prior experience with a tonal language, and background in musical training equated across groups. Half of the participants will be enrolled in first-year Mandarin at CMU (+instruction). The other half will be enrolled in first-year Spanish or French at CMU (-instruction). First-year Mandarin, Spanish, and French language courses are offered in Fall and Spring terms with 100 students completing each of these courses in 2017-2018. Instructors of each language group make use of the same, shared lesson plans and undergo thorough training to ensure uniformity. Our plan is to recruit participants across four academic semesters, presenting an excellent participant pool with the majority of enrolled students meeting inclusion criteria in recent semesters.

Protocol Details Common to All Participants. Pre-test Measures. Participants from each of the six groups (**Table I**) will undergo language, sensory, and cognitive assessments to examine factors that may interact with learning. Online Battery of Questionnaires. We will document participants' language background, dominant hand, musical training, and self-reported history of language

Carnegie Mellon University

disorders, speech impairments, videogame expertise, and self-reported hearing loss using batteries established by prior research. *Basic Hearing Screening*. We will measure participants' pure-tone frequency thresholds using the adaptive maximum likelihood procedure as implemented in the MLP MATLAB toolbox, which converges quickly (~30 trials). *Cognitive Tests*. Since auditory working memory and phonological ability are associated with language learning, we will use the Woodcock-Johnson Tests of Oral and Cognitive Abilities to evaluate phonological awareness, working memory and auditory working memory using the Sound Blending, Numbers Reversed and Auditory Working Memory subtests, as in prior research. These tests will be administered before training and/or classroom instruction commences to accommodate exclusion criteria and to match groups on music training. Pre-test measures will allow assessment of group differences and individual scores will be used as regressors in analyses to examine the relationship of individual differences to learning outcomes using linear mixed-effect regression models in R to capture both fixed effects of linguistic/cognitive background and training, as well as the random effects of participant.

Measures to Assess Learning. Whereas +instruction learners will have been explicitly instructed in Mandarin tone in the classroom, -instruction listeners will not. This marked difference impacts the methods available to assess learning, in part because naïve listeners cannot overtly label the tones. To meet this challenge, we employ three assessments that do not depend upon explicit knowledge. *(1) Perceptual Tasks: Pitch Pattern Discrimination (PPD) and Pitch Direction Identification (PDI) Tests.* Prior research has shown that participants who exhibit good Mandarin tone learning tend to exhibit better sensitivity to F0 contours in pitch contour discrimination and identification tests. These two measures will allow us to ascertain pre- to post- and delayed post-test change in Mandarin tone perception in a manner that can be readily applied across +/- instruction groups, and to assess perceptual weighting of pitch contour versus pitch height (and its change with learning). Additionally, these tests provide an assessment of individual differences in F0 sensitivity (pre-test). The PPD and PDI tests will follow the approach of our prior research. We will use the PPD data to calculate the sensitivity (d') and reaction time (offset of the second stimulus to response) of each participant at pre-test, post-test (after instruction/training), delayed post-test (3 months after training). We will use multidimensional scaling (MDS; Individual Differences Scaling, INDSCAL) with the PPD data to examine the underlying perceptual dimensions listeners use to discriminate tone contours. This MDS approach models successful prior research and provides us with a perceptual metric of the impact of learning across groups that do not depend on explicit awareness of tone. We will use the PDI data to calculate accuracy for each participant at pre-test, post-test, and delayed post-test.

(2) Artificial language-learning task. Previous research from our team has demonstrated the feasibility of using an artificial Mandarin-like tonal language to track and test learning across speakers with different levels of overt awareness of Mandarin tone, such as learners early in explicit classroom instruction (+instruction) compared to naïve learners (-instruction). PI [name] designed an artificial language that mimicked Mandarin's linguistic characteristics, including identical tone contours and syllable structures, but remained unintelligible to both English and Mandarin speakers. Because the artificial language was modeled on Mandarin, the results revealed not only how native speakers represent new Mandarin-like words, but also how non-native L2 learners acquire Mandarin-like tones in the context of the language acquisition task. In this multi-day

Carnegie Mellon University

training and testing paradigm, participants learn 130 consonant-vowel syllable+tone nonce words, each paired with a black and white nonce symbol. Daily learning is assessed through a 4-alternative forced choice (4AFC) task in which participants hear a target syllable+tone and click on a symbol. Feedback guides learning. This study also provides a way to compare online tonal sensitivity across Mandarin L2 learners and naïve learners with no prior experience with tone.

Protocol Details for Incidental Nonspeech Training. Training will take place in the videogame paradigm. Participants will train 60 min/week across 8 weeks for a total of 8 hours, online at their convenience. Our prior research demonstrates that overall time-on-task is closely related to the number of stimulus exposures in the videogame, even though participants differ in ultimate *gaming* achievements like Highest Level achieved. This is because at higher, faster levels "trials" are shorter with fewer stimulus repetitions, but there are more of them. Thus, our principal concern is with time-on-task and not with equating experience across listeners, *per se*. Protocol compliance will be monitored electronically and regular contact with our research team will be tailored to encourage high retention, as has been successful in our prior research. Learners will train on a set of nonspeech hums derived from a larger set of Mandarin talkers (N=20 instead of N=4 in Preliminary Study 2).

The training regimen we propose is substantially longer (8 hrs over 8 wks) than has been investigated in prior studies of incidental auditory category learning (~2.5 hrs in 5 days; 62). *This presents the opportunity to take a data-intensive approach.* We will use the continuous, fine-grained online data generated in the videogame to address the fundamental question of how categories are formed via incidental learning.

Protocol Details for Web-based Speech Training. Groups undertaking explicit speech training also will train 60 min/week across 8 weeks for a total of 8 hours. Training sessions will be broken into 20-minute modules, each of which takes place online. Protocol compliance will be monitored electronically and regular contact with our research team will be tailored to encourage high retention. Explicit speech training groups will train on standard L2 audio-lingual materials, which aim to develop learners' phonological awareness of tone. These tasks include same/different tone discrimination, AXB discrimination, 2-alternative-forced choice, 4-alternative-forced-choice, and tone labeling (roughly 4 minutes per task). Though the tasks are currently designed to be used by students enrolled in the university curriculum, all tasks are purely perceptual and do not require linguistic knowledge. For example, a participant must perceive *ma1* and *ma3* as different sounds but not necessarily understand that the former means 'mother' and the latter means 'horse.' As a result, the participants in the -instruction condition can perform the tasks without explicit knowledge of Mandarin. The stimuli will be modified to include speech from 20 speakers (thus matching the nonspeech hum stimuli). In addition to task accuracy, we will track time-on-task.

Protocol Details Specific to +instruction Learners. *Classroom Metrics.* We will collect metrics that include class attendance, self-reported study time, and self-reported classroom social network and interaction with Mandarin speakers. These metrics will allow us to compare and control for potential differences that may arise between +speech and +nonspeech groups. Importantly, the classroom instructor will be blind to each participant's assignment so as not to affect his/her performance. *Mandarin Tone Production.* Whereas -instruction, nonspeech learners train on perceptual representations relevant to Mandarin tone, they never explicitly encounter Mandarin

in the course of training. Thus, it is not possible to elicit Mandarin tone speech productions among -instruction learners. (However, speech production measurements will be possible in the Artificial Language Learning task administered post-training. This provides an across-group assessment of tone production). But, since all +instruction learners are instructed explicitly in Mandarin tone within the classroom environment it is possible to examine their tone productions across the course of the study. We will elicit speech productions from +instruction participants following the approach taken in Preliminary Study 2 using native-Mandarin raters, with associated acoustic analyses of the F0 contour to characterize these speech productions.

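### The power of .6 stated after 33% attrition does not follow from the named test, which gives about 0.81 with 102 completers

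*Combined protocol and SAP*

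**What the plan says.** All the inputs are in the combined protocol and SAP, mostly under Participants and Power.

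- **Size:** "We will test 150 participants (N=25/condition". The six cells are those of Table I (two classroom types by three training arms), and the section on details common to all participants confirms the count: "Participants from each of the six groups".
- **Test:** the sample was chosen so that "multiple regression analyses with all predictors have high power", given as 0.8 at two-tailed p<0.05 and f² = 0.08, to detect a "reliable deviation from 0 of a single linear regression coefficient (G*Power" calculation being the stated basis.
- **Allowance for dropout:** the sample is described as enlarged, "appreciating that we will need a somewhat larger sample to accommodate the potential for attrition across the retention interval".
- **After dropout:** "Even if we were to experience as much as 33% attrition, this sample size will assure a robust test (N=17", with f² again 0.08 and "power=.6) in line with prior research".

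The number of predictors is not given. No other test, alpha or subset of conditions is named for the .6.

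**The concern.** Effect size, alpha and test are fixed by the paragraph, so only the sample size changes between full enrolment and 33% loss. A fall to .6 is much steeper than the named test allows for that change.

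This sentence is the plan's only quantified statement of how the design withstands dropout, and the plan has a delayed post-test three months after training. As written, the design looks weak at 33% loss. If the named test is the intended one, that impression is wrong. If it is not, the paragraph misdescribes the calculation behind its figures. Either way, a reader cannot tell which test, N or alpha to trust.

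**Working it through.** **Inputs.** From Participants and Power: 150 enrolled, 25 per condition, f² = 0.08, two-sided alpha 0.05, one coefficient tested, 33% attrition, 17 left per condition. Six groups come from Table I. The total number of predictors p is not stated, so I assume 1 to 15 and show the range.

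**Completers.** 25 × 0.67 = 16.75, rounded to 17, and 17 × 6 = 102. The 17 cannot be a study total: that would be a loss of 1 − 17/150 = 89%, with power of about 0.19 (p = 1).

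**Formula.** For one coefficient in a multiple regression, the t statistic is noncentral t with noncentrality √(f² × N) and N − p − 1 degrees of freedom. Power is the probability that |t| exceeds the two-sided 5% critical value.

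**Trying to reproduce .6 at N = 102, p = 5.** The noncentrality is √(0.08 × 102) = √8.16 = 2.857, df = 96, the critical value is 1.985, and power is 0.807. The .6 is not reproduced.

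| N | p = 1 | p = 5 | p = 15 |
|---|---|---|---|
| 150 | 0.931 | 0.931 | 0.931 |
| 102 | 0.808 | 0.807 | 0.806 |
| 101 | 0.804 | 0.803 | 0.802 |
| 100 | 0.800 | 0.799 | 0.798 |
| 68 | 0.633 | 0.632 | 0.629 |
| 64 | 0.606 | 0.605 | 0.602 |

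The unstated p hardly matters: even 30 predictors give 0.804 at 102. A more conservative noncentrality, built on the residual degrees of freedom instead of N, gives 0.80 to 0.71 for 1 to 20 predictors, still not .6.

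**The 0.8.** The smallest N for power 0.80 is 101, and 1 − 101/150 = 32.7%. So 0.8 is consistent with a design target that 150 still meets after about 33% loss.

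**What would give .6 on the named test.**
- *Fewer completers:* power from 0.55 to below 0.65 needs 57 to 70 completers at p = 1 and 58 to 71 at p = 15. That is a loss of 1 − 71/150 = 53% to 1 − 57/150 = 62%.
- *Other inputs at N = 102, p = 5:* f² of 0.049 instead of 0.08, or alpha of about 0.011 instead of 0.05.

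**Calculations that come near the pair 0.8 and .6.**

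| Calculation | Full enrolment | After attrition | Departs from the text in |
|---|---|---|---|
| One coefficient, alpha 0.01, six groups | 0.80 (150) | 0.59 (102) | alpha |
| Joint F test of 4 coefficients, six groups | 0.79 (150) | 0.59 (102) | test |
| Joint F test of 3 coefficients, six groups | 0.83 (150) | 0.64 (102) | test |
| One coefficient, four conditions | 0.80 (100) | 0.63 (68) | N and conditions |

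The joint tests use noncentrality f² × N, alpha 0.05, and no predictors beyond those tested. The four conditions could be the trained cells of Table I without the two untrained controls ("A third group will serve as a control and undergo no additional training"), but the text ties its figures to 150 participants.

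**The case against.** The strongest reply is that 0.8 and .6 look like a coherent pair. A joint test of 3 or 4 coefficients, or a single coefficient at alpha 0.01, gives figures at or near both with all six groups. That suggests one unstated input behind both numbers more than a slip in one of them. Moreover, had the authors planned for about 101 completers, they should have expected about 0.8 after attrition, yet they wrote .6. On this view the 0.8 at 150 is also off (the named test gives 0.93), and the fault lies in how the test is described.

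This stands as a caution about cause, and it is why no cause is asserted here. It does not remove the error. Each alternative contradicts the single coefficient, the 0.05 or the 150 that the paragraph states. Reading the 0.8 as a target has support in the sentence on enlarging the sample. If it is instead read as the power at 150, it too needs correcting.

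A second reply is that the planned analysis is a linear mixed-effects model with random participant effects (Protocol Details Common to All Participants), so 0.81 is not the power of that analysis either. That is true, and 0.81 should not be presented as such. But the sponsor's own power statement rests on the regression test, and it is checked here on those terms.

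Third, the discrepancy is conservative on the named test and changes no procedure. That limits its weight to minor.

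**Conclusion.** The concern holds, as a minor error. With the test, effect size and alpha that the plan names, and 17 completers in each of six groups, power is about 0.81 against the stated .6, a gap of about 21 points. This rests on reading 17 as a per-condition figure and on a single coefficient tested across all six groups; it does not depend materially on the number of predictors. On those terms the design holds about 0.8 at 33% loss.

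The mismatch is certain; its cause is not. If fewer conditions, a stricter alpha or a joint test lay behind the .6, that figure may stand, but the paragraph then omits or misstates the inputs that produced it.

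**What to change.** Rerun G*Power once and correct the paragraph according to what was intended.

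- **If the test is one coefficient at two-sided 0.05 in all six groups:** replace the .6 with power of about 0.81 at 102 completers, and note 0.93 at 150.
- **Otherwise:** for each power figure, state the total N and the conditions counted, the alpha, and the numbers of tested and total predictors, and make the description of the test agree.

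In either case, say that the figures refer to the regression test and not to the mixed-effects model. The cost is one rerun and a small text correction, with no change to enrolment, procedures or analysis.

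### Assignment to training is never said to be random, and neither stated analysis has a class term if it is used for the instruction contrast

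*Combined protocol and SAP*

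**What the plan says.** The Design Overview sets out six cells: two instruction levels, fixed by the language course in which a student is enrolled, crossed with three training conditions. It does not say how students reach a training condition.

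Two statements bear on how groups are formed. Participants and Power requires "background in musical training equated across groups". The Pre-test Measures text under Protocol Details Common to All Participants says "These tests will be administered before training and/or classroom instruction commences to accommodate exclusion criteria and to match groups on music training". That training is assigned is clear from Protocol Details Specific to +instruction Learners, where "the classroom instructor will be blind to each participant's assignment so as not to affect his/her performance", but no method is given. The word random occurs only in describing a model term.

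Two analyses are mentioned. Participants and Power refers to multiple regression with all predictors. The Pre-test Measures text describes a mixed model in which "individual scores will be used as regressors in analyses to examine the relationship of individual differences to learning outcomes", and which is meant "to capture both fixed effects of linguistic/cognitive background and training, as well as the random effects of participant". Neither names a class, section or semester term, and neither is said to be the model for the instruction contrast.

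On outcomes, Measures to Assess Learning uses the pitch discrimination and identification tests (PPD, PDI) for "pre- to post- and delayed post-test change in Mandarin tone perception". For the artificial language, the Mandarin Tone Production text says that "speech production measurements will be possible in the Artificial Language Learning task administered post-training". No baseline of that task is described.

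**The concern.** Instruction follows enrolment, so that contrast is observational whatever is done. Training is the only factor that the investigators can assign, and so the only one that can support a causal claim. If assignment rests on music training alone, or on anything else short of chance, the training contrasts are protected only against differences that were measured and modelled. The arms differ in what they ask of a student: eight hours of videogame, eight hours of perceptual drill, or nothing. A difference in motivation between arms is therefore conceivable, above all between training and no training.

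The classroom metrics, collected to "compare and control for potential differences that may arise between +speech and +nonspeech groups", do not close the gap. They exist only for +instruction learners and accrue during the study.

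The second and lesser matter is the instruction contrast. Instruction is constant within a class. A model with participant as its only random effect, or an ordinary regression, treats classmates as independent and gives too small a standard error for that contrast if class outcomes are correlated.

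**Working it through.** **Inputs from the plan.** 150 participants, 25 per cell; hence 75 per instruction level and 50 per training condition (2 x 25). Four semesters. Two-sided 5% tests.

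**The plan's own figure.** The plan states no figure for bias or clustering. Its sample-size statement (power 0.8 at Cohen's f² = 0.08 for one coefficient) does not reproduce: N = 150 gives power 0.93, and 101 would suffice. That mismatch is a separate matter and does not bear on this point.

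**Allocation (all inputs assumed).** Let an unmeasured factor differ by δ = 0.25-0.5 SD between two arms and correlate c = 0.3-0.5 with the outcome.

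- No covariate: bias = δ x c. This runs from 0.25 x 0.3 = 0.075 to 0.5 x 0.5 = 0.25 SD.
- Pre-test covariate with pre-post correlation r, factor equally related to both: bias = δ x c x (1 - r), and the standard error is multiplied by √(1 - r²). At r = 0.5 the bias is 0.0375 to 0.125 SD; at r = 0.7 it is 0.0225 to 0.075 SD.

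Type I error from the noncentral t distribution:

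| | bias (SD) | 25 v 25 | 50 v 50 |
|---|---|---|---|
| no covariate | 0.075-0.25 | 5.8-13.9% | 6.6-23.6% |
| r = 0.5 | 0.0375-0.125 | 5.3-7.9% | 5.5-11.0% |
| r = 0.7 | 0.0225-0.075 | 5.1-6.5% | 5.3-8.1% |

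The first row is an upper bound within these assumptions, because the plan does use pre-test regressors. If the factor acts only on later learning, the pre-test gives no such reduction. Under random allocation the expected bias is 0.

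**Clustering (ICC and class counts assumed).** For k classes at a level, the design effect is 1 + (75/k - 1) x ICC. The variance inflation of the instruction contrast is the mean of the two levels' design effects, with 1 for a level that does not cluster. The standard error is understated by 1 - 1/√inflation, and type I error is 2 x (1 - Φ(1.96/√inflation)). With 8 Mandarin and 16 Spanish/French classes:

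| ICC | design effect, Mandarin / other | inflation, Mandarin only / both | SE too small by | type I error |
|---|---|---|---|---|
| 0 | 1 / 1 | 1 / 1 | 0 / 0 | 5% / 5% |
| 0.02 | 1.168 / 1.074 | 1.084 / 1.121 | 3.9% / 5.5% | 6.0% / 6.4% |
| 0.05 | 1.419 / 1.184 | 1.209 / 1.302 | 9.1% / 12.3% | 7.5% / 8.6% |
| 0.10 | 1.838 / 1.369 | 1.419 / 1.603 | 16.0% / 21.0% | 10.0% / 12.2% |

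Clustering in Mandarin classes only is the more plausible case, since the other courses teach no tone.

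**Semester.** A class intercept does not by itself remove semester differences. Assume semester shifts of -0.3, -0.1, 0.1 and 0.3 SD, Mandarin recruitment of 10, 15, 20 and 30, and the other level 30, 20, 15 and 10. The raw bias in the instruction contrast is 0.17 SD. Weighting classes as a random-intercept model would, at ICC 0.02-0.10 and with 4 + 8 or 8 + 16 classes, still leaves about 0.07-0.15 SD.

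**The case against.** The strongest reply is that the documents show silence, not a decision against randomisation. Blinding the instructor to assignment is quite compatible with random assignment. The music-training statements may concern the Mandarin and Spanish/French halves, which could be balanced only by matching. This stands. A reader might infer that the investigators chose a non-random design; the text does not support that. What remains is that it does not say that assignment is random, and music training is the only criterion it gives for any grouping.

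A reader might also infer that the artificial-language outcome is unprotected and take the no-covariate row as its likely error. That goes too far. The task has no stated baseline of its own, but the cognitive scores are planned regressors, and the PPD and PDI pre-tests are available as covariates. Nor do the documents give any imbalance. Scheduling would be a weak mechanism between the two trained arms, which both train online for 60 minutes a week over 8 weeks.

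On clustering, a reader might infer that the plan analyses instruction with a model that ignores classes. It names no model for that contrast, and the mixed model is introduced for individual differences, so the point is conditional. Larger figures need fewer classes. With 4 Mandarin and 8 other classes, understatement reaches 27% (Mandarin only) or 34% (both levels), and type I error 15% or 20%. But 4 Mandarin classes over four semesters is one per term. With 100 students completing the course in 2017-2018, split over two terms, that would be about 50 in a class. The text also speaks of instructors in the plural. Shared lesson plans and instructor training may keep the ICC small.

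**Conclusion.** The point holds in two parts of unequal weight.

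First, the method of assigning training is not stated, so its contrasts cannot be read as randomised. Unless assignment was random, they are open to unmeasured differences. The size is unknown; the bias range of 0.02-0.25 SD rests wholly on assumed imbalances and correlations, and its upper part applies only without useful covariates.

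Second, and only if one of the stated analyses is used for the instruction contrast and class ICC exceeds 0, that contrast's standard error is too small. On the assumed 8 + 16 classes and ICC 0.02-0.10, the understatement is about 4-16% (Mandarin classes only) or 5.5-21% (both levels), with type I error about 6-12%. Training can be crossed with class, so its contrasts are less affected.

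This is more than a missing detail, because a better method is available at almost no cost.

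**What to change.** 1. **Allocation.** After pre-test, randomise individuals 1:1:1 to the three training conditions by computer within instruction level and semester (2 x 4 = 8 strata, about 150/8 = 19 people each). Balance music training by minimisation with a random element. If allocation was already random, state how it was done. If it is complete and was not random, report the training contrasts as non-randomised.

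2. **Instruction contrast.** Record class section and add a class-section random intercept, with Satterthwaite or Kenward-Roger degrees of freedom. Keep the planned cognitive regressors, music training, and the outcome's own pre-test score where it exists. Use the PPD and PDI pre-tests as covariates for the artificial-language task. Recruit the two instruction levels in similar proportions each semester, or adjust for semester where the number of classes allows; do not claim that the class intercept absorbs semester. Report the contrast as observational.

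**Cost.** An allocation list, one recorded identifier and one model term. With 8 + 16 classes there are 24 - 2 = 22 between-class degrees of freedom (critical t 2.074, against 1.976 for 148). The standard error grows by about 4-27%, so the interval widens by about 9% (1.041 x 2.074/1.976 = 1.09) to 33% (1.266 x 2.074/1.976 = 1.33). Three semester terms would take a further 3 degrees of freedom, leaving 19; with 4 + 8 classes they would leave only 12 - 2 - 3 = 7. If the true ICC is 0, the test is slightly conservative (type I error about 3-4% in simulation).

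### If the participant random effects are fitted as an intercept, standard errors for PPD and PDI change and retention can be wrong in either direction; an unstructured visit covariance removes this cheaply

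*Combined protocol and SAP*

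**What the plan says.** All references are to the combined protocol and SAP.

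- **Model.** The paragraph on pre-test measures (Protocol Details Common to All Participants) will study the "relationship of individual differences to learning outcomes using linear mixed-effect regression models in R". Its fixed effects are linguistic and cognitive background and training, "as well as the random effects of participant". It does not say whether these are intercepts or also slopes, how time is coded, what the residual covariance is, or whether robust standard errors are used. No other repeated-measures regression model is given.
- **Outcomes.** Under Measures to Assess Learning, PPD is reduced to d' and a reaction time "of each participant at pre-test, post-test (after instruction/training), delayed post-test (3 months after training". For the other test: "We will use the PDI data to calculate accuracy for each participant at pre-test, post-test, and delayed post-test". That section says these measures serve to establish change from pre-test to post-test and delayed post-test. It attaches no model to those contrasts.
- **Spacing and size.** Design Overview: "We propose an 8-week training study among university students". The delayed test follows 3 months after training. Participants and Power: "We will test 150 participants (N=25/condition".

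**The concern.** With one value per person per visit, a full set of participant-by-visit random effects cannot be separated from residual error. The ordinary R fit is therefore a participant intercept. Such a model has one variance for all visits and one correlation for all pairs of visits, so a single pooled within-person error serves pre-post, pre-delayed and post-delayed alike.

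There is little reason to expect that equality here. The gaps differ (8 weeks, then 3 months), and 8 weeks of instruction or training fall inside the first gap but not the second. If the correlations or SDs differ, some contrasts get intervals that are too narrow (false claims of learning) and others get intervals that are too wide (missed differences in retention). The three-visit schedule exists to supply these contrasts.

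There is also a loss of precision. If the pre-test is an outcome row and the visit means are free in each group, the training comparison is a change score. That is less precise than adjusting for the pre-test already collected.

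**Working it through.** **The plan's own figure.** The only power figure concerns a "reliable deviation from 0 of a single linear regression coefficient (G*Power", with f² = 0.08, two-tailed 5% and stated power 0.8. With N = 150 the noncentrality is √(0.08 × 150) = 3.46 and power is 0.93, so the stated figure is not reproduced. The calculation contains no visit correlation, so this mismatch is a separate matter and does not enter below.

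**Inputs from the documents.** Three visits, one score per measure per visit, gaps of 8 weeks and 3 months (taken as 13 weeks, so 21 weeks from pre-test to delayed test), 25 per cell. **Assumed:** all SDs and correlations, since none is given; complete data.

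**Formula.** The change variance between visits j and k is v = s_j² + s_k² − 2·r·s_j·s_k. With free visit means and complete data, a random-intercept model uses the mean of the three change variances, v̄, for every contrast. So:

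- model SE / true SE = √(v̄ / v)
- real two-sided error at nominal 5% = 2·(1 − Φ(1.96 × ratio))

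**Pattern A: post and delayed scores most alike.** r = 0.5, 0.4, 0.8 (pre-post, pre-delayed, post-delayed), SDs 1. Then v = 1.0, 1.2, 0.4 and v̄ = 2.6/3 = 0.867.

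**Pattern B: correlation decays with time.** 8-week r = 0.7, SDs 1. Pre-delayed r = 0.7^(21/8) = 0.392; post-delayed r = 0.7^(13/8) = 0.560. Then v = 0.600, 1.216, 0.880 and v̄ = 2.696/3 = 0.899.

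| Contrast | A: ratio | A: real error | B: ratio | B: real error |
|---|---|---|---|---|
| Pre-post | √(0.867/1.0) = 0.93 | 6.8% | √(0.899/0.600) = 1.22 | 1.6% |
| Pre-delayed | √(0.867/1.2) = 0.85 | 9.6% | √(0.899/1.216) = 0.86 | 9.2% |
| Post-delayed | √(0.867/0.4) = 1.47 | 0.4% | √(0.899/0.880) = 1.01 | 4.8% |

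Simulating pattern A with six cells of 25 (3,000 runs) gave 7.1%, 9.0% and 0.4%.

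**Range over other assumptions** (pre-post, pre-delayed, post-delayed):

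- r = 0.6/0.5/0.8, equal SDs: 0.96, 0.86, 1.35
- r = 0.7/0.45/0.5, equal SDs: 1.22, 0.90, 0.95
- time decay, 8-week r from 0.6 to 0.9: 1.19 to 1.29, 0.88 to 0.83, 1.00 to 1.03
- all r = 0.6, SDs 1, 1.3, 1.3: 1.03, 1.03, 0.94
- all r equal, SDs equal: 1.00 throughout

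**What a ratio of 1.47 costs.** In pattern A, take a retention difference of 0.5 SD between two cells of 25. The true SE is √(0.4 × 2/25) = 0.179, and 0.5/0.179 = 2.80. Power with the right SE is Φ(2.80 − 1.96) = 0.80. With the model SE it is Φ(2.80 − 1.96 × 1.47) = 0.46.

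**Pre-test adjustment.** With equal SDs and pre-post correlation ρ, the adjusted variance is proportional to 1 − ρ² and the change-score variance to 2(1 − ρ). The ratio is (1 + ρ)/2. At ρ = 0.5 it is 0.75, so 25 per cell act like 25/0.75 = 33. At ρ = 0.8 it is 0.90, so they act like 25/0.90 = 28.

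**The case against.** **The direction.** A reader might infer that error bars for change are too narrow and those for retention too wide. The documents do not support that. It needs post and delayed scores to be the most alike pair, as in pattern A, or SDs that shrink after training. The unequal gaps alone point elsewhere: under decay the pre-post interval is too wide and the post-delayed one about right. Nor is pre-delayed always too narrow; with equal correlations and larger SDs after training its ratio is 1.03. This objection stands in full.

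**A slope is possible.** The plan says random effects in the plural and does not rule out a participant slope, which three visits can support. So one cannot say that the plan specifies a random-intercept model. But a slope is not a general cure. It has four covariance parameters against six unstructured. With a slope on weeks 0, 8 and 21, large-sample ratios (pre-post, pre-delayed, post-delayed) are 0.84, 0.95 and 1.42 in pattern A, where real pre-post error rises to 10%. In pattern B they are 1.04, 1.01 and 0.96. It mainly helps when correlation simply decays with time.

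**Stated purpose.** The mixed model is introduced for individual differences, not expressly for the visit contrasts. That is fair, and it rules out saying that a wrong model was chosen for them. Still, its fixed effects include training and its responses are learning outcomes. If it does not cover the visit contrasts, the plan gives no model for them.

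**Pre-test adjustment.** Change is a legitimate estimand, and the plan already intends to use individual pre-test scores as regressors, so adjustment may be partly envisaged. The gain also presumes that training allocation within an instruction level is unrelated to the pre-test score. The plan mentions assignment and matching on music training but not randomisation. That condition stands.

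**Conclusion.** The concern holds in conditional form. If the participant random effects are fitted as an intercept to one score per visit, the standard errors for change and retention are right only when all three change variances are equal, as they are with equal SDs and equal correlations. In the patterns checked, the ratio of model to true SE runs from 0.83 to 1.47, and the real error of a nominal 5% test from 0.4% to about 10%. The pre-post contrast can err either way. The pre-to-delayed contrast is too narrow under both the learning pattern and the decay pattern, which makes it the most exposed. All these sizes rest on assumed correlations and SDs and on complete data. They show what could happen, not what will.

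This is a cheap improvement, not a fatal flaw. The recommended model does not depend on which visit pattern is true, and little is lost if the correlations turn out equal.

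**What to change.** 1. For PPD d', PPD reaction time and PDI accuracy, write into the SAP a model with instruction x training x visit fixed effects and an unstructured 3x3 visit covariance, for example `gls` with `corSymm` and `varIdent`, or `mmrm`.
2. For training contrasts within an instruction level, use the post and delayed scores as outcomes, with own pre-test x visit as covariate. State how training is allocated, because this step relies on it.
3. Report the +/-instruction contrasts as unadjusted change as well. Participants choose their language course, so baseline differences there need not be chance.

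**Cost.** Six covariance parameters instead of two, that is four more, with 150 participants; a few lines of SAP text and a different R call. No new data are needed. One limit remains: the covariance is still shared by the six cells, so the change frees the pattern over visits but not differences between cells.
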